6.1.1 Investigational and control drugs

Study medication will be supplied in commercially available packaging labeled with "Zur klinischen Prüfung bestimmt". Eltrombopag and dexamethasone are both investigational drugs. Eltrombopag study drug will be provided as film-coated tablets.

Dexamethasone is the Standard of Care treatment and will be supplied as tablets. It will be provided through Novartis locally for treatment of patients enrolled in this study.

All investigational treatment is to be stored in a secure locked area while under the responsibility of the investigator. Receipt and dispensing of investigational and Standard of Care treatment must be recorded by an authorized person at the investigator's site.

Novartis	Confidential	Page 36
Amended Protocol Version 03 (Clean)		Protocol No. CETB115JDE01

For detailed safety information refer to the [ETB115 Investigators Brochure, current edition] and the approved product labeling. A description of the study treatment, dose, frequency, and method of administration of eltrombopag and dexamethasone is provided in Table 6-3.

rusio o o invooligational and control arug			
Study treatments	Pharmaceutical form and route of administration	Dose	Frequency and/or Regimen
Eltrombopag	Tablet for oral use	25 mg	Daily
Eltrombopag	Tablet for oral use	50 mg	Daily
Dexamethasone	Tablet for oral use	40 mg	Daily

 Table 6-3
 Investigational and control drug

6.1.2 Additional study treatments

No other treatment beyond investigational drug and control drug are included in this trial.

6.1.3 Treatment arms/group

Patients will be randomized at visit Week 1 Day 1 to one of the following 2 treatment arms/groups in a ratio of "1:1"

- Arm A: Eltrombopag + a short course of high-dose of dexamethasone
- Arm B: 1-3 cycles of high-dose dexamethasone

For detailed treatment guidance refer to Section 6.1.

6.1.4 Treatment duration

Arm A: The treatment duration for all patients in Arm A (eltrombopag QD for 26 weeks + high-dose dexamethasone QD for 4 consecutive days starting at day 1 and limited to 1 cycle) will be 26 weeks (6 months) including 6 weeks tapering period. All patients who discontinue study treatment as per study design with platelet counts $\geq 30 \times 10^{9}$ /L in the absence of bleeding or use of any rescue therapy will be followed for response assessments till Week 52 after study start. Patients who relapse after eltrombopag discontinuation before Week 52 will reinitiate treatment with eltrombopag till Week 52 and will discontinue from study at Week 52. Patients with platelet counts < 30×10^{9} /L after 26 weeks of treatment with eltrombopag will continue treatment as summarized in Table 6-1 and discontinue from study at Week 52.

Arm B: The maximum duration of treatment with dexamethasone for all patients in Arm B will be 12 weeks. All patients who discontinue study treatment as per study design with platelet counts $\geq 30 \times 10^9/L$ in the absence of bleeding or use of any rescue therapy will be followed for response assessments till Week 52. Patients who relapse (platelet count $< 30 \times 10^9/L$) after dexamethasone discontinuation before Week 52 will be treated with eltrombopag as summarized in Table 6-2 and discontinue the study at Week 52. Patients with platelet count $< 30 \times 10^9/L$ after 3 cycles with dexamethasone will initiate treatment with eltrombopag and discontinue the study at Week 52.

6.2 Other treatment

Not applicable.
6.2.1 Concomitant therapy

The patient must be told to notify the investigational site about any new medications he/she takes after the start of the study treatment. All medications (other than study drug) and significant non-drug therapies (including physical therapy and herbal/natural medications) administered after the enrollment of the patient in this study must be listed on the Concomitant Medications or the Procedures and Significant Non-Drug Therapies electronic case report form (eCRF).

Each concomitant drug must be individually assessed against all exclusion criteria/prohibited medication. If in doubt the investigator should contact the Novartis medical monitor before randomizing a subject or allowing a new medication to be started. If the subject is already enrolled, contact Novartis/sponsor to determine if the subject should continue participation in the study.

6.2.1.1 Permitted concomitant therapy requiring caution and/or action

HMG-CoA Reductase Inhibitors (statins)

Patients will be permitted to use HMG-CoA reductase (3-hydroxy-3-methyl-glutaryl-CoA) inhibitors during the study, but these drugs should be used with caution and a 50% dose reduction of the HMG-CoA reductase inhibitor is recommended, with close monitoring for safety, such as liver chemistry and signs and symptoms of myolysis, and efficacy, such as cholesterol and triglycerides (refer to individual product information for monitoring recommendations).

Polyvalent Cations (Chelation)

Eltrombopag chelates with polyvalent cations such as aluminum, calcium, iron, magnesium, selenium and zinc. Eltrombopag should be taken at least 2 hours before or 4 hours after any products such as antacids, dairy products, or mineral supplements containing polyvalent cations to avoid significant reduction in eltrombopag absorption.

Food Interaction

To avoid significant reduction in eltrombopag absorption, eltrombopag should be taken at least two hours before or four hours after food containing > 50 mg calcium and at least one hour before to two hours after food containing little (< 50 mg) (or preferably no) calcium. The administration of a single 50 mg dose of eltrombopag with a standard high-calorie, high-fat breakfast that included dairy products led to reduced eltrombopag exposure. Foods low in calcium (defined as < 50 mg calcium per serving) including fruit, lean ham, beef and unfortified (no added calcium, magnesium, iron) fruit juice, unfortified soy milk, and unfortified grain did not significantly impact plasma eltrombopag exposure, regardless of calorie and fat content.

Substrates of OATP1B1 or BCRP

Concomitant administration of eltrombopag and other OATP1B1 or breast cancer resistance protein (BCRP) substrates should be undertaken with caution.

Examples of drugs which are OATP1B1 or BCRP substrates are given in Appendix 16.1.

CYP and UGT inhibitors and inducers

Eltrombopag is metabolised through multiple pathways including CYP1A2, CYP2C8, UGT1A1, and UGT1A3. Medicinal products that inhibit or induce a single enzyme are unlikely to significantly affect plasma eltrombopag concentrations; whereas medicinal products that inhibit or induce multiple enzymes have the potential to increase (e.g. fluvoxamine) or decrease (e.g. rifampicin) eltrombopag concentrations.

Confidential

6.2.2 **Prohibited medication**

Patients must abstain from using investigational or not use marketed drugs without a well-known safety profile and from using prohibited prescription or nonprescription drugs within 30 days or 5-half-lives (whichever is longer) prior to the first dose of study treatment and until completion of follow-up procedures unless, in the opinion of the Investigator and Sponsor, the medication will not interfere with the study.

Patients must abstain from taking herbal supplements within 7 days (or 14 days if the drug is a potential enzyme inducer) or 5-half-lives (whichever is longer) prior to the first dose of study treatment until completion of the 30-day follow-up visit, unless the Investigator and Sponsor agree that the medication will not interfere with the study treatment.

Drugs that affect platelet function (including but not limited to, aspirin, clopidogrel and/or nonsteroidal anti-inflammatory drugs [NSAIDs]) should not be taken during the study unless there is a very clear indication and the Investigator documents the rationale. This is due to the fact that they may affect the results of the bleeding scale assessments.

Please refer to locally approved SmPC of dexamethasone for information regarding prohibited concomitant medication.

6.2.3 Rescue medication

Any ITP-directed medication or therapy, other than randomized treatment, given during the treatment phase of the trial with the aim to increase platelet count for the subjects who have clinically significant bleeding will be considered a rescue therapy and must be recorded on the appropriate eCRF page. A subject who receives rescue medication or therapy will not be considered in having achieved sustained response off treatment for the primary endpoint. Any ITP-directed medication or therapy given during the follow-up phase after treatment discontinuation until week 52 will be considered non-responders for the primary endpoint.

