12.5.1 Efficacy endpoints

1. To compare the ability of eltrombopag in combination with a short course of high-dose dexamethasone **to induce overall response (OR)** after treatment discontinuation at week 52 versus a defined course of dexamethasone

Number (%) of patients with platelet count $\ge 30 \times 10^{9}$ /L and a 2-fold increase of screening platelet count after treatment discontinuation in the absence of bleeding events \ge Grade II and no rescue therapy at all visits until Week 52 will be provided, analysis will be equivalent to the primary endpoint analysis.

- 2. To assess the **duration of sustained response off treatment**, median duration of response off treatment (weeks) counted from last dose of study treatment (eltrombopag or dexamethasone) until loss of response will be calculated using a Kaplan-Meier analysis.
- 3. .
- 4. To assess the ability of eltrombopag to induce overall response (OR) by week 4

Number (%) of patients with platelet count $\ge 30 \times 10^9$ /L and a 2-fold increase of screening platelet count at least once within the first 4 weeks without bleeding events \ge Grade II and no rescue therapy will be provided, analysis will be equivalent to the primary endpoint analysis.

- 5. To assess the ability of eltrombopag to induce a **complete response (CR) by week 4** Number (%) of patients with platelet count $\geq 100 \times 10^{9}$ /L at least once within the first 4 weeks without bleeding events \geq Grade II and no rescue therapy will be provided, analysis will be equivalent to the primary endpoint analysis.
- 6. To assess the **platelet count** from screening to baseline and to 1, 2, 4, 12, 26 and 52 weeks; absolute and relative change in platelet count from screening to baseline and to 1, 2, 4, 12, 26 and 52 weeks and EOS will be provided. Box plots for absolute and/or relative change in platelet counts from screening to baseline and to different time points will also be provided.
- 7. To assess the time to response for overall and complete response using a Kaplan-Meier analysis.
- 8. To assess the duration of response for overall and complete response using a Kaplan-Meier analysis.

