#### 2.4.2 Prior, concomitant and post therapies

The FAS will be used for the analyses below.

The number of subjects using rescue treatments as defined in section 6.2.3 of the CSP will be summarized by treatment group for the periods pre-randomization, during on-treatment period and after on-treatment period. Listings will display the kind and duration of all ITP-directed pre-treatments and rescue medications separately.

For analyses of rescue medication (e. g. dose, time point, etc.) the Data Review committee decided which doses of dexamethasone, eltrombogag and other ITP-directed therapies were used as rescue medication and as study treatment. Concomitant medications (of any type, i.e. classified as rescue medication or not) and significant non-drug therapies prior to and after the start of the study treatment will be listed and summarized according to the Anatomical Therapeutic Chemical (ATC) classification system, by treatment group.

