### 2.5 Analysis of the primary objective

#### 2.5.1 Primary endpoint

The primary objective is to compare the ability of both study treatments to induce sustained response off treatment at 52 Weeks.

The primary endpoint is the proportion of patients with sustained response off treatment at 52 weeks (i.e. until study visit Week 53).

Sustained response off treatment is defined as:

- reach platelet count  $\ge 30 \times 10^9$ /L and then maintain platelet counts  $\ge 30 \times 10^9$ /L after discontinuation of study treatment AND
- maintain platelet count  $\ge 30 \times 10^{9}$ /L in the absence of bleeding events  $\ge$  Grade II AND
- without the use of any rescue therapy (see Section 6.2.3 of CSP) until week 52

Details on Response or non-response are assessed during the Data Review Meeting and documented accordingly.

For the primary and supportive analyses the FAS will be used.

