### 2.7 Analysis of secondary efficacy objective(s)

#### 2.7.1 Secondary endpoints

For all analyses on secondary parameters the FAS is used unless it is specified otherwise.

The following parameters are analysed analogeously to the analysis of primary parameter respectively the supportive analyses on the primary parameter:

- 1) **Overall response** (OR), defined as number (%) of patients with platelet count  $\geq 30 \times 10^9$ /L and a 2-fold increase of screening  platelet count after treatment discontinuation in the absence of bleeding events  $\geq$  Grade II and no rescue therapy at all visits until Week 52 will be provided, analysis will be equivalent to the primary endpoint analysis
- 2) The duration of sustained response off treatment, median duration of response off treatment (weeks) counted from last dose of study treatment (eltrombopag or dexamethasone) until loss of response will be provided calculated using a Kaplan-Meier analysis based on the population
- 3) Overall response (OR) by week 4, presented by number (%) of patients with platelet count  $\ge 30 \times 10^{9}$ /L and a 2-fold increase of screening platelet count at least once

<sup>4 For patients who were pre-treated: the platelet count directly before start of pre-treatment

within the first 4 weeks without bleeding events  $\geq$  Grade II and no rescue therapy will be provided, analysis will be equivalent to the primary endpoint analysis.

- 4) Complete response (CR) by week 4, presented by Number (%) of patients with platelet count  $\geq 100 \times 10^{9}$ /L at least once within the first 4 weeks without bleeding events  $\geq$  Grade II and no rescue therapy will be provided, analysis will be equivalent to the primary endpoint analysis.
- 5) **Platelet count** from screening to 1, 2, 4, 12, 26 and 52 weeks; absolute and relative change in platelet count to screening, 1, 2, 4, 12, 26 and 52 weeks and EOS will be provided. Box plots for absolute and/or relative change in platelet counts from baseline to different time points will also be provided.
- 6) The **time to response for overall and complete response** using a Kaplan-Meier analysis.
- 7) The **duration of response for overall and complete response** using a Kaplan-Meier analysis. Here the following population is used: FAS patients who reached overall respectively complete response.

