#### 2.7.3 Handling of missing values/censoring/discontinuations

Missing values are not replaced.

The time to response is censored with the date of the patient's last visit.

The duration of response is censored with the date of the patient's last visit.

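### Treatment-phase rescue is tied to clinically significant bleeding, so ITP therapy given for a low count alone could be credited as a Week 4 response or set the time to response

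*Protocol*

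**What the plan says.** Protocol 6.2.3 has two rules.

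- Treatment phase: ITP-directed therapy other than randomised treatment, given "with the aim to increase platelet count for the subjects who have clinically significant bleeding will be considered a rescue therapy".
- Follow-up phase: there is no bleeding condition, but the rule is confined to one endpoint. Patients given any ITP-directed therapy "after treatment discontinuation until week 52 will be considered non-responders for the primary endpoint".

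Overall response (OR) and complete response (CR) by Week 4 need one qualifying count, "at least once within the first 4 weeks without bleeding events" of Grade II or worse (Protocol 12.5.1), and no rescue. SAP 2.7.1 repeats this: "Grade II and no rescue therapy will be provided, analysis will be equivalent to the primary endpoint analysis". For time to response, SAP 2.7.3 gives a single rule: "The time to response is censored with the date of the patient's last visit".

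The SAP takes its definition of rescue from the protocol. SAP 2.4.2 summarises rescue as defined in 6.2.3, and the primary endpoint in SAP 2.5.1 requires response "without the use of any rescue therapy (see Section 6.2.3 of CSP) until week 52". It then describes a process: "the Data Review committee decided which doses of dexamethasone, eltrombogag and other ITP-directed therapies were used as rescue medication and as study treatment" (SAP 2.4.2). SAP 5.5.1 starts from the investigator's yes/no items and has the data review meeting consider whether each classification is reasonable. SAP 5.5.4 and 5.5.5 leave the dates of reaching and losing OR and CR to the committee's minutes.

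SAP 5.1 includes, among the reasons for stopping eltrombopag, its use as rescue in patients randomised to dexamethasone alone.

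**The concern.** OR and CR by Week 4 and time to response are meant to show what the randomised treatment achieves. The no-rescue condition is the only part of their definitions that removes the effect of other platelet-raising therapy. As 6.2.3 words it, that condition applies to patients with clinically significant bleeding, some of whom the Grade II bleeding clause already excludes. It does not reach a patient without such bleeding who is given IVIg or extra steroid because the count is low.

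That situation is foreseeable. Protocol 1.1.1 says that counts below 20 to 30 × 10⁹/L typically trigger treatment whatever the bleeding, and lists IVIg among first-line options. Section 6.2.2 does not name IVIg or steroids as prohibited. If such a patient's count then rises, the written rules allow it to be reported as a response to study treatment. Whether it is reported that way depends on a committee judgement for which no criterion is written down.

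**Working it through.** **The plan's own figure.** Protocol 12.8.1 expects about 24 patients and a power of about 24%; the Amendment 3 rationale gives 12 per group. For 30% versus 65%, n = 12 per arm, two-sided 5%, with continuity correction:

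z = (0.35 − 1/12 − 1.96·√(2·0.475·0.525/12)) / √((0.30·0.70 + 0.65·0.35)/12) = (0.350 − 0.083 − 0.400)/0.191 = −0.70, so power = 24.3%.

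The stated figure reproduces, and this point does not change it. It is shown only to fix 12 per arm as the basis below.

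**Rules side by side.**

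| Therapy | Protocol 6.2.3, read literally | What the SAP adds |
|---|---|---|
| IVIg or non-protocol steroid, treatment phase, clinically significant bleeding | Rescue | Nothing different |
| IVIg or non-protocol steroid, treatment phase, low count alone | Not rescue | Committee decides; no criterion |
| Arm A second-line therapy, count below 30 after 4 weeks at 75 mg (Table 6-1) | Primary non-response if counted as follow-up; not rescue for secondary endpoints | Committee decides; no criterion |
| Arm B eltrombopag for a count below 30 (Table 6-2) | Same as the row above | Called rescue in SAP 5.1 |

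The last two rows are both triggered by a count. Only the Arm B case is called rescue, so the written rules could treat the arms differently.

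**Timing.**

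- Dexamethasone cycle 1: Days 1–4.
- First protocol step for a count that stays low: Day 15 in Arm A (eltrombopag increase after 2 weeks, Protocol 6.5.1), and Day 15 at the earliest in Arm B (second cycle at the shortest 14-day interval, counted start to start).
- Interval with no protocol step: Days 5–14, i.e. 14 − 5 + 1 = 10 days.
- Scheduled counts after baseline through Week 5 Day 1 (Table 8-1): Days 8, 15, 22 and 29, so four chances to meet a criterion that needs one. Day 8 lies in the interval.
- Table 6-1 second-line therapy in a patient starting at 50 mg: no earlier than Day 15 + 28 = Day 43. That is after Week 4, so it bears on time to response and not on the Week 4 rates.

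**Size.** The documents give no frequency of count-only therapy. With 12 per arm:

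- One affected patient: 1/12 = 8.3 points. Two: 2/12 = 16.7 points.
- With a and b affected patients in Arms A and B, the between-arm difference shifts by (a − b)/12. For an assumed 0 to 2 per arm, that is −16.7 to +16.7 points, and zero if a = b.
- Illustration with an assumed 8/12 in both arms: one affected patient in Arm A gives 9/12 versus 8/12, an unadjusted odds ratio of (9/3)/(8/4) = 1.5. Two give (10/2)/(8/4) = 2.5.

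**The case against.** The strongest reply is that, in operation, rescue was never limited to bleeding.

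- SAP 2.4.2 has the committee sort ITP-directed therapies into rescue and study treatment. IVIg cannot be study treatment, so on that split it falls under rescue.
- SAP 5.1 applies the word rescue to count-triggered eltrombopag.
- SAP 2.5.4 lists bleeding and rescue as separate reasons for non-response.
- Each patient's medication was reviewed (SAP 5.5.1), and the one example of an overruled classification moves therapy towards rescue.
- Protocol 6.1.2 says that no other treatment is included in the trial, and 6.2.1 requires each concomitant drug to be checked against the exclusion criteria and prohibited medication.
- Protocol 1.1.1 says steroids generally work within 2 weeks, so waiting until Day 15 is normal. The study with recurrent IVIg in Protocol 4.5.2 concerned patients who had already been treated.

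Much of this stands. The SAP conflicts with 6.2.3; it is not uniformly bleeding-only. The committee's minutes are not in these documents, and nothing shows that any patient was misclassified. But a process is not a criterion. SAP 2.4.2 and 2.5.1 still point to 6.2.3, and where the committee's practice and the stated definition differ, a reader cannot tell which was applied.

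A reader might also take the phrase "classified as rescue medication or not" in SAP 2.4.2 as permission to leave ITP-directed therapy out of rescue. It is not: it only says that the summary by drug class covers all concomitant medication.

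**Conclusion.** The point holds as a gap and an inconsistency in the definition. Followed literally, 6.2.3 allows a count raised by IVIg or non-protocol steroid, given for a low count alone, to be credited as OR or CR by Week 4. It also allows that therapy, or Table 6-1 second-line therapy, to set the time to response. The 8.3 points per affected patient rests on 12 patients per arm; the number affected is unknown and may be zero.

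Two stronger conclusions are tempting and are not supported. One is that the reported response rates are inflated: the committee may have classed all such therapy as rescue. The other is that the primary endpoint is biased. The treatment-phase wording applies there too, but any ITP-directed therapy after discontinuation is already non-response, the count must hold off treatment to Week 52, and no bias is shown. Pre-treatment before randomisation is a separate matter.

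Severity is minor to moderate. All analyses are descriptive, but that makes the reported rates themselves the result.

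**What to change.** In Protocol 6.2.3 and the SAP sections that use it (2.4.2, 2.5.1, 2.7.1, 2.7.3, 5.5.1, 5.5.4, 5.5.5), delete the bleeding condition. Define rescue as any ITP-directed therapy outside the scheduled randomised regimen, from first dose to Week 52, whatever the indication.

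- **Scheduled regimen.** Arm A: eltrombopag with protocol dose adjustments and taper to Week 26, plus one dexamethasone cycle. Arm B: 1–3 dexamethasone cycles. Re-initiated, continued or switched eltrombopag is outside it.
- **OR and CR by Week 4.** Keep the requirement of no rescue within the first 4 weeks.
- **Time to response.** Do not credit counts obtained after such therapy starts. A patient with no earlier response has no event and is censored at the last visit, as now.
- **Duration of overall and complete response.** Treat the start of such therapy as loss of response.
- **Reporting.** Apply the same definition in the committee's check of the roughly 24 patients, and report rescue by arm and by trigger (bleeding or count only).

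The change affects classification, not when sites may treat. The data are on the forms listed in SAP 5.5.1. SAP 3.0 was agreed before database lock and signed shortly after, and its reviews are described as done, so existing classifications need rechecking. If the committee already worked this way, recording the criterion is nearly all that is needed.

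Downsides to state: a Week 4 rate may fall by 8.3 points per affected patient, and a genuine later response after such therapy is not credited. The wider definition also makes count-only therapy in the treatment phase a primary non-response, unless the sponsor limits the change to the secondary endpoints. That choice should be explicit.
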